5.6 Concomitant medications

In general, the use of any concomitant medication/therapies deemed necessary for patient supportive care and safety are permitted. Other anticancer agents, specifically systemic chemotherapy, radiation therapy, or biologic response modifiers are not permitted during the study. Intrathecal chemotherapy is allowed if intended for prophylaxis. No other investigational drug is allowed during the study. Prophylaxis may be used for the prevention of infections or nausea and vomiting.

Subjects may be receiving systemic corticosteroids (daily doses \leq 10 mg of prednisone or equivalent if indicated for adrenal replacement or antiemetic therapy), topical, or inhaled corticosteroids at study enrollment. They may receive systemic, topical, inhaled, or enteric corticosteroids while on study without limitation if they develop conditions that require corticosteroid therapy; such subjects are not required to discontinue study participation. The dose and amount of steroids that the patient receives will be recorded in the case report form.

All ongoing medications and therapies (including herbal products, nutritional supplements, and nontraditional medications) at screening will be considered prior medications. Concomitant medication data will not be collected or entered into the case report form other than steroids as mentioned above; however, the subject's medication record will contain a list of concomitant medications.

6.0 PATIENT EVALUATION

6.1 Pre-Treatment Evaluation: All pretreatment studies should be obtained within 14 days (± 3 days) of entry into the trial, unless otherwise stated.

1. A complete history and physical, including assessment of baseline adverse events.
2. CBC, platelet count, differential (differential can be omitted if WBC is $\leq 0.5 \times 10^9/L$).
3. Creatinine, total bilirubin, ALT, amylase, lipase.
4. Pregnancy test (urine or plasma) in females of childbearing potential should be performed within 24 hours of initiation of treatment.
5. Bone marrow aspirate during the last 14 days preceding study initiation. Cytogenetics will be obtained prior to therapy in patients known to have cytogenetic abnormalities at the time of diagnosis or relapse (results from prior analysis within 4 weeks can be used for this purpose).
6. Chest x-ray.
7. Pretreatment optional correlative studies will be collected on a companion protocol PA13-0291(Appendix C). Every effort will be made to collect all samples at all time-points for all patients; however, missing collection in one or more of these time points in occasional patients will not be considered a protocol deviation/violation.
8. Flow cytometry for MRD (peripheral blood and/or bone marrow) within 14 days.
9. Baseline TSH, Free T4 within 30 days of starting treatment.

6.2 Evaluation During Treatment: All tests are ± 5 days unless otherwise specified.

1. Physical exam before administration of nivolumab for the first cycle, then every 4 weeks (± 7 days) for 2 cycles, then every 8-12 weeks until end of 6 cycles of therapy. Patients who continue therapy beyond 6 months will continue having physical exam every 2-3 months while on therapy.
2. Assessment of adverse events every month (assessment may be by phone interview) while on therapy and approximately 30 days after end of therapy.
3. CBC, platelet count, differential (differential can be omitted if WBC is $\leq 0.5 \times 10^9/L$) once weekly for the first cycle, then every 2 weeks for two cycles, then every 4 weeks (± 1 week).

4. Creatinine, total bilirubin, ALT once weekly for the first cycle, then every 2 weeks for two cycles, then every 4 weeks (± 1 week). Amylase and lipase once per cycle.
5. TSH and Free T4 level every 3 months (± 1 month) for the first 6 months (± 1 month) and then every 6 months thereafter while on study.
6. Bone marrow aspiration on day 28 (± 7 days), then every 2 cycles (± 1 cycle) for 6 cycles, then every 3 months; then as clinically indicated. Bone marrow aspirations to be performed at MDACC.
7. Flow cytometry for MRD (peripheral blood and/or bone marrow) every 2 cycles (± 1 cycle) for 6 cycles, then every 3 months; then as clinically indicated.
8. Correlative studies (Appendix C). Every effort will be made to collect all samples at all-time points for all patients; however, missing collection in one or more of these time points in occasional patients will not be considered a protocol deviation/violation.
9. Patients who complete therapy will be followed as clinically indicated after the end of therapy. If treatment is resumed follow-up will be done according to the follow-up schedule that was being done at the time they discontinued therapy.

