3.0 STUDY POPULATION

3.1 Inclusion Criteria

1. Patients with AML in remission (defined as CR, CR with incomplete platelet recovery –CRp-, CR with incomplete hematologic recovery -CRi-, or partial remission defined as a bone marrow with <10% blasts after therapy with or without hematologic recovery).
2. High risk for relapse defined as:
 - a. 1st CR with high risk features for relapse (including history of prior malignancy treated with chemotherapy or radiotherapy, or history of myelodysplastic syndrome, myeloproliferative disorder, chronic myelomonocytic leukemia, MDS/MPN or other hematologic malignancy thought to have evolved to AML [i.e., secondary AML, sAML]; high risk cytogenetics at diagnosis; FLT3 mutated at diagnosis; or presence or minimal residual disease assessed by PCR, cytogenetics, and/or flow cytometry at time of enrollment)
 - b. 2nd CR regardless of disease characteristics at the time of diagnosis.
3. Have received induction chemotherapy and at least one cycle of consolidation chemotherapy. Patients should have achieved a CR within 12 months of enrollment onto protocol.
4. No further chemotherapy or SCT planned at the time of enrollment.
5. Age 18 years or older.
6. Adequate organ function: creatinine \leq 1.5 x ULN; serum bilirubin \leq 1.5 x ULN; AST and ALT \leq 2.5 x ULN.
7. ECOG performance status \leq 2
8. Females of childbearing potential must have a negative serum or urine beta human chorionic gonadotrophin (β -hCG) pregnancy test result within 24 hours prior to the first dose of treatment and must agree to use an effective contraception method during the study and for 23 weeks after the last dose of the study drug. Females of non-childbearing potential are those who are postmenopausal greater than 1 year or who have had a bilateral tubal ligation or hysterectomy.

9. Males who have partners of childbearing potential must agree to use an effective contraceptive method during the study and for 31 weeks following the last dose of study drug
10. Patients or their legally authorized representative must provide written informed consent.

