5.1.6 Dose Modification

Dose reductions or dose escalations are not permitted.

5.2 Dose Delay Criteria:

Because of the potential for clinically meaningful nivolumab-related AEs requiring early recognition and prompt intervention, management algorithms have been developed for suspected AEs of selected categories.

Dose delay criteria apply for all drug-related adverse events

Nivolumab administration should be delayed for the following:

- Any Grade \geq 2 non-skin, drug-related AE, with the following exceptions:
 - Grade 2 drug-related fatigue or laboratory abnormalities do not require a treatment delay, However, dose delays should occur for the following laboratory abnormalities:
 - G2 Creatinine, or
 - G2 ALT, AST or total bilirubin
- Any Grade 3 skin, drug-related AE
- Any Grade 3 drug-related laboratory abnormality, with the following exceptions for lymphopenia, leukopenia, AST, ALT, total bilirubin, or asymptomatic amylase or lipase:
 - Grade 3 lymphopenia or leukopenia does not require dose delay.
 - Grade 3 AST, ALT or total bilirubin requires permanent discontinuation of nivolumab
- Any AE, laboratory abnormality, or intercurrent illness which, in the judgment of the investigator, warrants delaying the dose of study medication.

5.3 Criteria to Resume Treatment:

Subjects may resume treatment with study drug when the drug-related AE(s) resolve to Grade ≤ 1 or baseline value, with the following exceptions:

- Subjects may resume treatment in the presence of Grade 2 fatigue
- Subjects who have not experienced a Grade 3 drug-related skin AE may resume treatment in the presence of Grade 2 skin toxicity
- Drug-related pulmonary toxicity, diarrhea, or colitis, must have resolved to baseline before treatment is resumed
- Drug-related endocrinopathies adequately controlled with only physiologic hormone replacement may resume treatment

If the criteria to resume treatment are met, the subject should restart treatment at the next scheduled timepoint per protocol. However, if the treatment is delayed past the next scheduled timepoint per protocol, the next scheduled timepoint will be delayed until dosing resumes.

If treatment is delayed > 6 weeks, the subject must be permanently discontinued from study therapy, except as specified in discontinuation section.

5.4 Management Algorithms:

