Immuno-oncology (I-O) agents are associated with AEs that can differ in severity and duration than AEs caused by other therapeutic classes. Nivolumab is considered an immuno-oncology agent in this protocol. Early recognition and management of AEs associated with immuno-oncology agents may mitigate severe toxicity. Management algorithms have been developed to assist investigators in assessing and managing the following groups of AEs: Gastrointestinal, Renal, Pulmonary, Hepatic, Endocrinopathies, Skin, Neurological.

For subjects expected to require more than 4 weeks of corticosteroids or other immunosuppressants to manage an AE, consider recommendations provided in the algorithms. These algorithms are found in Appendix B of this protocol. The guidance provided in these algorithms should not replace the Investigator's medical judgment but should complement it.

5.5 Discontinuation Criteria:

Treatment should be permanently discontinued for the following:

- Any Grade 2 drug-related uveitis or eye pain or blurred vision that does not respond to topical therapy and does not improve to Grade 1 severity within the re-treatment period OR requires systemic treatment
- Any Grade 3 non-skin, drug-related adverse event lasting > 7 days, with the following exceptions for drug-related laboratory abnormalities, uveitis, pneumonitis, bronchospasm, diarrhea, colitis, neurologic adverse event, hypersensitivity reactions, and infusion reactions:
 - Grade 3 drug-related uveitis, pneumonitis, bronchospasm, diarrhea, colitis, neurologic adverse event, hypersensitivity reaction, or infusion reaction **of any duration** requires discontinuation
 - Grade 3 drug-related laboratory abnormalities do not require treatment discontinuation except those noted below:
 - Grade 3 drug-related thrombocytopenia > 7 days or associated with bleeding requires discontinuation
 - Grade 3 drug-related ALT, AST or total bilirubin require discontinuation:
- Any Grade 4 drug-related adverse event or laboratory abnormality, except for the following events which do not require discontinuation:
 - Isolated Grade 4 amylase or lipase abnormalities that are not associated with symptoms or clinical manifestations of pancreatitis and decrease to < Grade 4 within 1 week of onset.

- Isolated Grade 4 electrolyte imbalances/abnormalities that are not associated with clinical sequelae and are corrected with supplementation/appropriate management within 72 hours of their onset

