6.3 End of Treatment Visit

To be completed 30 days (+/- 7 days) after the last dose of study drug.

During this visit the following procedures will be performed:

Physical exam

Assessment of adverse events

CBC with differential and platelets

Creatinine, total bilirubin, ALT

Bone marrow aspiration (if not done within 6 weeks and if feasible)

Flow cytometry for MRD

Correlative studies (optional; missing optional studies collection will not be considered a protocol deviation)

If the patient is unwilling or unable to do end of study visit at MDACC, an

assessment of adverse events may be done by phone and every attempt should be made to collect required studies from other institution if available.

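### AST can by itself bar entry, delay a dose or end treatment, but none of the section 6 chemistry lists schedules it

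*Combined protocol and SAP*

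**What the plan says.** Four statements in the combined protocol and SAP act on AST:

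- Section 3.1, criterion 6 (organ function) requires "AST and ALT \leq 2.5 x ULN".
- Section 5.2 lists "G2 ALT, AST or total bilirubin" among the laboratory findings that require a dose delay.
- Section 5.2 also states "Grade 3 AST, ALT or total bilirubin requires permanent discontinuation of nivolumab".
- Section 5.5 repeats the stopping rule: "Grade 3 drug-related ALT, AST or total bilirubin require discontinuation".

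Three lists in section 6 set the chemistry tests:

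- 6.1 item 3, before treatment: "Creatinine, total bilirubin, ALT, amylase, lipase".
- 6.2 item 4, on treatment: "Creatinine, total bilirubin, ALT once weekly for the first cycle, then every 2 weeks for two cycles, then every 4 weeks", with amylase and lipase once per cycle.
- 6.3, end of treatment: "Creatinine, total bilirubin, ALT".

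Section 5.3 lets a patient resume once a drug-related event has returned to Grade 1 or lower, or to the baseline value. Section 5.4 refers investigators to Appendix B for management algorithms, including a hepatic one. That appendix is not in the supplied text.

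**The concern.** A rule can be applied only to a value that someone has measured. The delay and discontinuation rules join ALT, AST and bilirubin with an or, so AST alone is enough to trigger them. The section a site uses to order its tests leaves AST out.

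The case at risk is an AST rise to Grade 2 or above while ALT and bilirubin stay below threshold. Under section 6 as written, that rise need not be seen. The missed action would be a required delay or, at Grade 3, a required permanent stop. Two further effects follow:

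- **Resumption.** After an AST-triggered delay, 5.3 may need a baseline AST, and section 6 does not ask for one.
- **Toxicity monitoring.** Section 9.0 counts treatment-related, clinically significant non-hematologic events of Grade 3 or higher. An unmeasured AST rise that met that definition would not enter the count.

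**Working it through.** The plan gives no figure to reproduce. The check sets the rules against the schedule, then counts the cost of the remedy.

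**Step 1. Rules against lists**

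| Analyte | Eligibility (3.1) | Grade 2 delay (5.2) | Grade 3 discontinuation (5.2, 5.5) | 6.1 item 3 | 6.2 item 4 | 6.3 |
|---|---|---|---|---|---|---|
| ALT | yes | yes | yes | yes | yes | yes |
| Total bilirubin | yes | yes | yes | yes | yes | yes |
| Creatinine | yes | yes | not named | yes | yes | yes |
| AST | yes | yes | yes | no | no | no |

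AST is in 3 of 3 rule types and 0 of 3 lists. It is the only one of the four analytes without a scheduled measurement, and no other section in the supplied text schedules it.

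**Step 2. Would something else bring the value in?**

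- At screening, yes by implication: criterion 6 cannot be confirmed without an AST.
- On treatment, the rules presuppose a value and the investigator is free to order one, but no schedule calls for it.
- The monthly adverse-event assessment (6.2 item 2) may be done by phone, so it is no substitute for a laboratory result.

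**Step 3. Can the documents size the problem?**

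Only loosely. Table 2.4.2.4-1 (Phase 1 study, treatment-related select events) gives:

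- All doses: any hepatic event in 18 of 306 and ALT increased in 11 of 306. The difference is 18 − 11 = 7, and 7/306 = 2.3%.
- 3 mg/kg, the dose used here: 3 of 54 and 1 of 54. The difference is 3 − 1 = 2, and 2/54 = 3.7%.
- Higher-grade column: 4 against 1 over all doses, and 2 against 0 at 3 mg/kg.

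So hepatic events were recorded that the ALT term did not account for, including at this dose. The table does not say whether they were AST, bilirubin or another term. A patient with a low-grade ALT rise and a higher-grade AST rise would also be counted under ALT. The differences are therefore neither a rate nor a strict ceiling for isolated AST rises.

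**Step 4. Number of added assays**

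The inputs are the 6.2 item 4 frequencies, 4-week cycles (4.2.1), 6 cycles and a maximum of 30 patients (9.0).

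- Cycle 1, weekly: 4
- Cycles 2–3, every 2 weeks: 2 × 2 = 4
- Cycles 4–6, every 4 weeks: 3
- On treatment: 4 + 4 + 3 = 11
- Plus 1 pre-treatment and 1 end-of-treatment: 11 + 2 = 13 per patient
- All patients: 13 × 30 = 390

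This assumes every patient completes 6 cycles. If the pre-treatment draw also serves as the first cycle 1 draw, the figures are 12 per patient and 12 × 30 = 360.

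**The case against.** The strongest reply is that this is a drafting omission with a narrow consequence. Sections 3.1, 5.2 and 5.5 name AST as a threshold, which presupposes that it is measured. Sections 5.2 and 5.5 also let the investigator act on any laboratory abnormality, and the unseen Appendix B may call for AST. ALT and bilirubin are drawn weekly, then every 2 weeks, then every 4 weeks, and should catch most hepatic events. Harm needs an isolated AST rise and no AST ordered. The 6.3 addition does little for the dosing rules, because that visit falls about 30 days after the last dose. A phone call would miss a silent ALT rise just as easily.

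Much of this stands:

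- The scenario is narrow, and eligibility is largely covered in practice.
- The phone provision shows only that the adverse-event assessment is no backstop; it is not a fault in itself.
- The 6.3 edit is the least needed of the three. Its use is to keep the safety follow-up consistent with the on-treatment tests.

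Two things do not follow. A threshold in section 5 is not a schedule, and a site that performs every test in section 6 has complied without having an on-treatment AST. Section 5.4 presents Appendix B as help with assessing and managing adverse events, not as a laboratory schedule, although its content could not be checked.

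**Conclusion.** The concern holds. AST can by itself exclude a patient, delay a dose or end treatment, and the section 6 chemistry lists do not provide for measuring it. The effect is confined to isolated AST rises, mainly on treatment, and their frequency cannot be taken from the documents. The primary endpoint, its analysis, the sample size and the stopping boundaries are untouched. The point is still worth correcting, because one of the affected actions is a mandatory permanent stop and the remedy costs very little. The conclusion rests on the supplied text, without Appendix B, and on a site doing what section 6 lists and no more.

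**What to change.** Add AST next to ALT in 6.1 item 3, 6.2 item 4 and 6.3, run on the same blood sample. If only two edits are made, they should be 6.1 and 6.2, which serve the eligibility, delay, discontinuation and resumption rules.

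The cost is three small wording edits and one extra assay at each chemistry draw: the 13 per patient counted above through 6 cycles, then one every 4 weeks for those who continue. No new visit, blood draw or change to the analysis is needed.

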6.3 End of Treatment Visit

To be completed 30 days (+/- 7 days) after the last dose of study drug.

During this visit the following procedures will be performed:

Physical exam

Assessment of adverse events

CBC with differential and platelets

Creatinine, total bilirubin, ALT

Bone marrow aspiration (if not done within 6 weeks and if feasible)

Flow cytometry for MRD

Correlative studies (optional; missing optional studies collection will not be considered a protocol deviation)

If the patient is unwilling or unable to do end of study visit at MDACC, an

assessment of adverse events may be done by phone and every attempt should be made to collect required studies from other institution if available.

7.0 CRITERIA FOR RESPONSE

The primary endpoint of this study is the rate of sustained remission at 6 months from the start of study treatment.

Response criteria will be modified from the International Working Group for AML (JCO 2003; 21: 4642-9). Responders are patients who obtain a CR, CRi, or PR, with or without cytogenetic response, hematologic improvements, and morphologic leukemia-free state. Briefly, criteria are as follows:

Complete Remission (CR):

- ◆ **Peripheral blood counts:**

Neutrophil count $\geq 1.0 \times 10^9/L$
Platelet count $\geq 100 \times 10^9/L$

- ◆ **Bone marrow aspirate and biopsy:**

$\leq 5\%$ blasts
No Auer rods
No extramedullary leukemia

Complete remission with incomplete blood count recovery (CRi):

- ◆ **Peripheral blood counts:**

Neutrophil count $< 1.0 \times 10^9/L$, or
Platelet count $< 100 \times 10^9/L$

- ◆ **Bone marrow aspirate and biopsy:**

$\leq 5\%$ blasts
No Auer rods
No extramedullary leukemia

Partial Remission (PR):

- ◆ All CR criteria if abnormal before treatment except:
- ◆ $\geq 50\%$ reduction in bone marrow blast but still $> 5\%$

Morphologic Leukemia-Free State (MLF):

- ◆ Bone marrow: $\leq 5\%$ myeloblasts

Hematologic Improvement (HI): Hematologic response must be described by the number of positively affected cell lines.

- ◆ **Erythroid response (E)** (pretreatment Hgb <11 g/dL):
 - Hgb increase by ≥ 1.5 g/dL
- ◆ **Platelet response (P)** (pretreatment platelets $<100 \times 10^9/L$):
 - Absolute increase of $\geq 30 \times 10^9/L$ for patients starting with $>20 \times 10^9/L$ platelets, or
 - Increase from $< 20 \times 10^9/L$ to $> 20 \times 10^9/L$ and by at least 100%
- ◆ **Neutrophil response (N)** (pretreatment ANC $<1.0 \times 10^9/L$)
 - At least 100% increase and an absolute increase $>0.5 \times 10^9/L$
- ◆ **Blast response (B):**
 - At least 50% reduction in blast percentage.

Relapse: Morphologic relapse after CR is defined as a reappearance of leukemic blasts in the peripheral blood $>10\%$ or $> 5\%$ blasts in the bone marrow not attributable to any other cause (eg, bone marrow regeneration after consolidation therapy). The appearance of new dysplastic changes should also be considered relapse. In the setting of recent treatment, if there are no or few (e.g, $<5\%$) circulating blasts and the bone marrow contains 5% to 20% blasts, a repeat bone marrow performed at least a week later is necessary to distinguish relapse from bone marrow regeneration. In such instances the date of recurrence is defined as the first date that more than 5% blasts were observed in the marrow. The reappearance or development of cytologically proven extramedullary disease also indicates relapse. Molecular and/or genetic relapse is characterized by reappearance of a cytogenetic or molecular abnormality.

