1.0 OBJECTIVES

1.1 Primary Objectives:

1. To evaluate the anti-leukemic effects of Nivolumab in patients with Acute Myeloid Leukemia (AML) who have achieved a 1st complete remission (CR) after induction chemotherapy and consolidation chemotherapy and have high risk for relapse, or have achieved a 2nd CR. The primary endpoint is defined as recurrence-free survival (RFS) rate at 6 months.

1.2 Secondary Objectives:

1. To evaluate the immunologic responses to Nivolumab among patients with AML in CR status post standard chemotherapy
2. To determine whether response to Nivolumab correlate with immunologic responses.
3. To evaluate assessment of Minimal Residual Disease (MRD) by flow cytometry as a predictor of response to immune therapy in treatment of AML and changes during the course of therapy with nivolumab
4. To evaluate time to relapse and overall survival
5. To evaluate the toxicity profile of Nivolumab among patients with AML in CR

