For the primary analysis of the efficacy endpoint, we will use Kaplan-Meier methodology to compute the RFS rate at 6 months and the 95% confidence interval. As a secondary analysis, we will perform a competing risk analysis treating stem cell transplant as a competing event for RFS." . The Kaplan-Meier method will be used to estimate the median RFS time and the probability of overall survival. Expressions of immune mediated markers will be summarized with descriptive statistics: means medians, ranges, and standard deviations. Two-sample t test or Wilcoxon rank sum test will be used to compare the expressions of markers between patients remaining in CR and patients having recurrence disease. Scatterplots will be used to explore possible associations between clinical responses and the immunomodulatory markers. Spearman correlation coefficients will be computed to evaluate the association between MRD and immunomodulatory markers, as well as the association between MRD and the changes in marker expressions pre and post treatment.

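### Every patient entering in CR, CRp or CRi already meets the Section 7.0 responder definition, so it cannot serve secondary objectives 2 and 3 and conflicts with the marker contrast in Section 9.0

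*Combined protocol and SAP*

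**What the plan says.** Section 7.0 first gives a maintenance outcome as the primary endpoint: remission still held six months after study treatment began. It then adds a response definition adapted from published AML criteria: "Responders are patients who obtain a CR, CRi, or PR, with or without cytogenetic response, hematologic improvements, and morphologic leukemia-free state". No baseline state, assessment time or minimum duration is attached.

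Section 3.1, item 1, sets the entry state: "Patients with AML in remission (defined as CR, CR with incomplete platelet recovery –CRp-, CR with incomplete hematologic recovery -CRi-, or partial remission", the last of these being "partial remission defined as a bone marrow with <10% blasts after therapy with or without hematologic recovery".

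Two secondary objectives in Section 1.2 depend on the term. Item 2 reads "To determine whether response to Nivolumab correlate with immunologic responses". Item 3 asks whether MRD by flow cytometry predicts response.

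Section 9.0 uses two different outcomes for the markers. A t test or rank-sum test compares patients who stay in CR with patients whose disease recurs. Separately, "Scatterplots will be used to explore possible associations between clinical responses and the immunomodulatory markers". MRD is correlated with markers and with marker changes, but not with any clinical outcome.

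**The concern.** The responder sentence suits the treatment of active leukemia, where reaching CR is the achievement. Here remission is the ticket of entry and keeping it is the aim. A patient whose disease does nothing at all is in CR at the day-28 marrow (Section 6.2) and counts as a responder. So does a patient in CR at day 28 who relapses at month 3.

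At stake are two secondary objectives. A variable that takes nearly the same value in everyone cannot correlate with an immune marker or be predicted by MRD. With two incompatible outcomes in the plan, the choice between them could also be made after the data are seen.

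**Working it through.** **1. Entry state against responder state.** Section 3.1 gives no count thresholds for CR, CRp or CRi, so I assume the Section 7.0 thresholds apply. Section 7.0 CR needs neutrophils of at least 1.0, platelets of at least 100 (both ×10⁹/L) and no more than 5% marrow blasts. CRi keeps the marrow condition with either count below its limit, so it also covers CRp.

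| Entry state | Section 7.0 state before dose 1 | Responder if entry status counts | Responder only if the state is newly reached |
|---|---|---|---|
| CR | CR | Yes, on day 0 | No route by improvement |
| CRp or CRi | CRi | Yes, on day 0 | Only by moving to CR |
| Partial remission, blasts >5% and <10% | Not automatically a responder state | Not automatically | By reaching CR or CRi |

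The first reading makes every CR, CRp and CRi entrant a responder. The second makes response impossible for a CR entrant whom the drug keeps in remission. Neither measures maintenance benefit.

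**2. Partial-remission entrants.** Section 7.0 PR requires at least a 50% "reduction in bone marrow blast but still" above 5%. Take the study-entry marrow as reference, with blast percentage b and 5 < b < 10. A fall of at least 50% leaves at most b/2, and b/2 < 10/2 = 5. The result cannot also exceed 5%, so these patients cannot reach Section 7.0 PR from their entry value; they can respond only through CR or CRi. If the reference is the marrow before induction, they may meet PR at entry. The protocol does not say which applies, and gives no expected share of such patients.

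**3. Where the term is used.** Objectives 2 and 3 and the Section 9.0 scatterplots use response with no definition other than Section 7.0. The sample size, futility rule and primary Kaplan-Meier analysis use RFS.

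**4. What the alternative contrast yields.** Inputs from Section 9.0: exponential RFS, median 8 months, at most 30 patients, and 25% possibly leaving for transplant.

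- The plan's own figure: S(6) = 0.5^(6/8) = 0.5946, which reproduces the stated 59.5%.
- All 30 followed: 30 × 0.5946 = 17.8 in remission and 30 − 17.8 = 12.2 with an event, about 18 versus 12.
- With 25% removed for transplant before six months: 30 × 0.75 = 22.5; 22.5 × 0.5946 = 13.4 and 22.5 − 13.4 = 9.1, about 13 versus 9.
- Under the Section 7.0 label with entry status counted: no non-responders among CR, CRp and CRi entrants.

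**5. Objective 3.** Of the MRD analyses in Section 9.0, none has relapse, RFS or response as the outcome. Objective 3 therefore lacks both a discriminating response variable and an analysis.

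**The case against.** The best defence is that little in the plan rests on the responder sentence. Section 7.0 opens with the right outcome and goes on to define relapse. The Section 9.0 marker comparison uses a staying-in-remission contrast, and everything confirmatory uses RFS. This largely stands, and it rules out several stronger readings.

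- A reader might infer that the response objectives cannot be answered. For objective 2 that is wrong: Section 9.0 supplies a workable contrast. It lacks a time point, but that is a matter of wording.
- A reader might infer that essentially every patient is a responder at entry. The documents support this only for CR, CRp and CRi entrants; step 2 shows why partial-remission entrants differ.
- A reader might expect a published response rate near 100%. Section 9.0 plans no response rate.
- A reader might hold that the marker comparison drops patients who stay in CRi or CRp. Literally they fall in neither group. But the protocol often uses CR loosely: Section 3.1, item 2, sorts all eligible patients into first or second CR. The text needs clarifying; exclusion is not shown.
- The blast-response item, "At least 50% reduction in blast percentage", has no minimum baseline, so a fall from 2% to 1% would qualify. It is tempting to put a chance rate on this, but the documents give neither the number of cells counted nor typical blast levels. The item is also an optional component that does not decide responder status.

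The defence does not reach objective 3 or the undefined clinical responses in the scatterplots, and it leaves the two outcome definitions in conflict.

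**Conclusion.** The point holds as a definitional defect confined to secondary objectives, and it should be corrected. All CR, CRp and CRi entrants meet the Section 7.0 responder definition on day 0, assuming Section 3.1 uses the same thresholds. Objective 3 is hit hardest. Objective 2 is only partly affected, since the existing contrast would give roughly 18 versus 12 patients, or 13 versus 9 after transplant losses. Those splits assume full enrolment, the plan's exponential model with an 8-month median and, for the smaller one, that all 25% leave before six months with the rest keeping the same rate. No primary design figure changes.

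**What to change.** **Section 7.0.** Replace the responder sentence with the maintenance outcome: *response means being alive without relapse, as defined in this section, six months after the first dose*. State that the non-relapsed group comprises CR, CRp and CRi. Reconcile the classification of patients entering in partial remission: relapse is defined after CR with a marrow threshold of more than 5%, which some of them may exceed on day 0.

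**Section 9.0.**

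- Use this one outcome for objective 2, objective 3, the marker comparison and the plots.
- A bare yes/no at six months cannot classify a patient transplanted in remission before then. Relate markers to RFS as a time-to-event outcome, censoring at transplant as in the primary analysis, or state another rule consistent with it.
- Add an analysis of baseline MRD against RFS for objective 3.
- Report improvement only where there is room for it: CRi or CRp to CR, and MRD-positive to MRD-negative.

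**Cost.** Wording in two sections and a little extra analysis. Baseline MRD (Section 6.1) and relapse status are already collected, so no new patients or samples are needed. The responder rate as now defined could no longer be reported.
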